10.3.11.4 Safety data

Safety data will be evaluated by changes in vital sign measurements and the frequency and severity of AEs. Concomitant medication will be recorded for safety.

Adverse events:

The Investigator is responsible for monitoring the safety of patients who have enrolled in the study. All AEs considered to be possibly related to Ampion will be followed until the event resolves or stabilized without further change. Patients will be followed for the occurrence of AEs until 12 weeks after the first dose of study medication.

Investigators are required to document all AEs occurring during the clinical trial, commencing with the first day of treatment and including the protocol-defined post-treatment follow-up period on the appropriate CRF pages.

The severity of AEs (mild, moderate, severe), relatedness (related, possibly related, unrelated) along with the duration, action taken, and outcome (e.g., study withdrawal) will also be recorded. In addition, events meeting the criteria of a SAE) must be reported to the Sponsor within 24 hours on the SAE reporting forms.

10.3.11.5 Efficacy data:

All efficacy variables will be assessed at Baseline (Day 0), Week 2 (Day 14 ± 7), Week 4 (Day 30 ± 7), Week 6 (Day 42 ± 7), Week 8 (Day 56 ± 7), Week 10 (Day 70 ± 7) and Week 12 (Day 84 ± 7). For analysis of baseline WOMAC A pain, the baseline pain score is the average of all scores measured during days -7 to 0, prior to injection of treatment. For analysis of week 12 WOMAC A pain, the week 12 pain score is the average of all scores measured during the seven days prior to and including the Week 12 office visit.

All statistical tests will be two-sided, except the co-primary endpoints which require superiority in pain vs. saline control in pain and superiority to baseline in function.

Unless otherwise specified, continuous variables will be summarized with the number of non-missing observations, mean, standard deviation, median, minimum, and maximum displayed. Categorical data will be summarized as counts and percentages. All efficacy assessments will be summarized as the measured value and as the change from Baseline by treatment at each timepoint. Summary statistics will include number of observations, mean, standard deviation, median, minimum and maximum. Change from Baseline will also include a 95% confidence interval.

Except where otherwise specified, missing data will not be estimated or carried forward in any of the descriptive analyses. No multiple comparison adjustment will be made for the secondary

efficacy analyses. Data transformation or use of rank-based tests may be used if endpoints depart substantially from a normal distribution.

Baseline is defined as the last pre-treatment assessment.

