10.4.2 Secondary Endpoints

- Change in PGA between Baseline and Week 12
- Change in the 100 mm VAS Pain Scale between Baseline and Week 12
- Use of rescue analgesia (amount of acetaminophen used between Baseline and Week 12)
- Incidence and severity of treatment-emergent adverse events (TEAEs)

A serial gatekeeping approach will be used to test the secondary endpoints in a sequential manner (i.e. PGA, 100 mm VAS, rescue analgesia).

The difference between treatment groups in the mean change in PGA from Baseline to Week 12 will be analyzed using a similar MMRM model, with Treatment assignment, Week, and Baseline value as fixed effects and including patient as a repeated measure with a compound symmetric covariance matrix for residuals.

The difference between treatment groups in the mean change in 100 mm VAS from Baseline to Week 12 will be analyzed using a similar MMRM model, with Treatment assignment, and Baseline value as fixed effects and including patient as a repeated measure with a compound symmetric covariance matrix for residuals.

The difference between treatment groups in the amount of acetaminophen used between Baseline and Week 12 will be analyzed with a Wilcoxon rank-sum test.

All secondary efficacy analyses will be reported with one sided p-values and successively compared to a critical level of 0.025 if each preceding test was significant.

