## **8. STATISTICAL METHODS OF ANALYSIS**

### **8.1 General Principles**

Data will be summarized by saline and Ampion arms. Descriptive statistics on continuous variables will include mean, standard deviation, median, 25th and 75th percentiles, and range. Change from Baseline will include a 95% confidence interval. Categorical variables will be summarized using frequency counts and percentages. Data listings of individual patient's data will be provided.

Statistical testing for the primary endpoints of pain and function will be performed using a one-sided p-value compared to  $\alpha=0.025$ .

Other efficacy analyses will be presented with one-sided p-values. Safety analyses will be presented as two-sided.

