### **8.6.7 Multiplicity Adjustment**

Hierarchical testing for the ITT analysis population will be applied to the analysis of the primary endpoints. It will also be utilized for the secondary endpoints, assuming significance of the co-primary effectiveness endpoints are established. Given significance

for the primary effectiveness tests (WOMAC A and WOMAC C (as specified)), then and only then would PGA score be tested at the one-sided alpha of 0.025; if the PGA score is significant then and only then, will the 100 mm VAS hypotheses be tested at a one-sided alpha of 0.025; if the 100 mm VAS hypothesis is significant then, and only then, will the amount of rescue analgesia through Week 12 be tested at a one-sided alpha 0.025. Multiplicity adjustment will not be applied to exploratory endpoints.

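### Protocol 10.3.11.5 contradicts protocol 10.4.2 on multiplicity and sidedness for the secondary endpoints; the SAP shows the intent, but the conflicting rule was never withdrawn

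*Protocol*

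**What the plan says.** **Protocol 10.3.11.5 (Efficacy data)** gives two general rules. On sidedness: "All statistical tests will be two-sided, except the co-primary endpoints". On multiplicity: "No multiple comparison adjustment will be made for the secondary" efficacy analyses. Neither sentence makes an exception for the secondary-endpoint section, and no two-sided significance level is given.

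**Protocol 10.4.2 (Secondary Endpoints)** gives the opposite rules for the same analyses. On multiplicity: "A serial gatekeeping approach will be used to test the secondary endpoints in a sequential manner (i.e. PGA, 100 mm VAS, rescue analgesia"). On sidedness and level: "All secondary efficacy analyses will be reported with one sided p-values and successively compared to a critical level of 0.025", provided each preceding test succeeded. It does not say explicitly that the sequence opens only after both co-primaries succeed.

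**The SAP** takes the 10.4.2 side throughout. Section 8.1 says: "Other efficacy analyses will be presented with one-sided p-values". Section 8.6.2 repeats one-sided testing for the secondaries. Section 8.6.7 opens the sequence only after both co-primaries are significant and tests PGA first; then "if the PGA score is significant then and only then, will the 100 mm VAS hypotheses be tested", and rescue analgesia comes last, each at one-sided 0.025. Exploratory endpoints are unadjusted. SAP section 9, on changes from the protocol's analyses, does not mention the conflict.

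**The concern.** Both protocol sections speak of the secondary efficacy analyses, so they govern the same three tests, and nothing in the protocol says which section prevails. The case that exposes the conflict is ordinary: PGA misses 0.025 while VAS or rescue use falls below it. Under 10.4.2 and SAP 8.6.7 the sequence stops and no claim follows. Under 10.3.11.5 nothing stops it. Someone writing the study report could cite the protocol for either position once the data are known.

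The sidedness conflict has a second, smaller effect. SAP 8.1 makes all other efficacy p-values one-sided, which reaches the exploratory and subset analyses. The protocol's only exception to two-sided testing is the co-primaries. On those analyses the two documents disagree, and 10.4.2 does not settle it because it covers only the secondaries.

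**Working it through.** **The rules side by side**

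| Question | Protocol 10.3.11.5 | Protocol 10.4.2 | SAP |
|---|---|---|---|
| Multiplicity, secondaries | none | serial gatekeeping | fixed sequence (8.6.7) |
| Gate on co-primaries | not mentioned | not explicit | explicit (8.6.7) |
| Sidedness, secondaries | two-sided, no level stated | one-sided, 0.025 | one-sided (8.1, 8.6.2), 0.025 (8.6.7) |
| Sidedness, exploratory and subset | two-sided; only the co-primaries excepted | not covered | one-sided (8.1) |

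**Inputs.** Three secondary efficacy endpoints (protocol 10.4.5 gives the count); one-sided level 0.025 (10.4.2, SAP 8.6.7). Assumed, because the documents do not give them: correlations of 0 to 0.8 between the test statistics, and a two-sided level of 0.05 where 10.3.11.5 is silent.

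**1. The plan's own level.** In a fixed sequence under the global null, any false rejection requires the first test to reject. The family-wise error therefore equals the level of the first test, 0.025. Simulation (2,000,000 draws per correlation) gave 0.0248 to 0.0251, so the stated 0.025 reproduces.

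**2. No adjustment, one-sided 0.025 each, no co-primary gate.** If independent: 1 − (1 − 0.025)³ = 1 − 0.975³ = 0.0731. The Bonferroni bound is 3 × 0.025 = 0.075. Simulated with equal correlations:

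| Assumed correlation | Ungated | Gated |
|---|---|---|
| 0 | 7.3% | 2.5% |
| 0.3 | 6.8% | 2.5% |
| 0.5 | 6.2% | 2.5% |
| 0.8 | 4.9% | 2.5% |

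**3. The disputed case alone.** PGA not significant, but at least one of VAS and rescue significant, all null and independent: 0.975 × (1 − 0.975²) = 0.975 × 0.0494 = 0.048. This is the whole difference between 7.3% and 2.5%.

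**4. Sidedness.** One-sided 0.025 and two-sided 0.05 have the same critical value in the direction favouring Ampion, z = 1.960. At those levels the two rules give the same secondary decision. For a symmetric test with an estimate favouring Ampion, the one-sided p-value is half the two-sided one, so the printed number differs.

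**5. Effect on the design.** With a pain difference of 0.83 − 0.62 = 0.21 and SD 0.85, 90% power needs 690 patients in total at either one-sided 0.025 or two-sided 0.05, as the protocol states. Power is 97.8% with 517 per arm and 97.2% with 492 per arm, against the stated 97%. The conflict does not touch sample size or the co-primary tests.

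**The case against.** The strongest reply is that the SAP settles the matter. It is written for this protocol version, states one rule for the secondaries in three places, and agrees with the protocol section dedicated to them. Protocol 10.1 leaves the comprehensive presentation to the analysis plan, and 10.3.10 says a final SAP will be issued before interim unblinding. This largely stands. A reader might infer that the confirmatory status of a secondary result is open in practice; the documents do not support that, because the operational rule can be read without difficulty. What remains is that no text gives the SAP precedence, protocol 11.3 requires a written amendment for any protocol change, and SAP section 9 is silent.

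A second reply is that no adjustment may mean only that alpha is not split, which is true of a fixed sequence. SAP 8.6.7 files that sequence under a multiplicity-adjustment heading, so the reading does not remove the conflict. It is fair, though, that 10.3.11.5 never says an unadjusted result supports a claim; it only fails to block one.

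A third reply is that sidedness changes nothing that matters. For secondary decisions this holds at a two-sided level of 0.05. A reader might pair the two-sided p-value of 10.3.11.5 with the 0.025 of 10.4.2 and infer a critical value of 2.241, or an effective one-sided level of 0.0125. Neither document prescribes that hybrid: 10.4.2 attaches 0.025 to one-sided p-values only.

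**Conclusion.** The contradiction is real, and the rule in 10.3.11.5 is wrong as written. Its practical weight is moderate, because the SAP consistently adopts the gated one-sided sequence.

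The size is a family-wise error for the three secondaries of 7.3% if independent, or about 5% to 6% at assumed correlations of 0.8 to 0.5, against 2.5% with gating. These are global-null rates with no co-primary gate, so they describe what the no-adjustment sentence would allow, not what the SAP plans.

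Two further inferences should be resisted:

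- Ungated two-sided tests at an assumed 0.05 give 1 − 0.95³ = 14.3% if independent, counting both directions. Setting this against 2.5% is not like for like; the matching gated figure is 5%.
- One-sided exploratory p-values do not conceal a result favouring saline. Such a p-value would be near 1, and SAP 8.6 already presents treatment differences with 95% confidence intervals.

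The sidedness conflict is therefore one of reporting for the secondaries. For the exploratory and subset analyses it is an unresolved protocol–SAP disagreement without confirmatory consequence. The co-primary analysis and sample size are unaffected.

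**What to change.** - **Protocol 10.3.11.5, multiplicity.** Delete the no-adjustment sentence. State instead that the secondary endpoints follow the fixed order of 10.4.2, each at one-sided 0.025, only once both co-primaries are significant, and that exploratory endpoints carry no adjustment. This also brings the co-primary gate, now explicit only in SAP 8.6.7, into the protocol.
- **Protocol 10.3.11.5, sidedness.** Extend the exception to two-sided testing so that it covers the three gated secondaries as well as the co-primaries.
- **SAP 8.1.** Reconcile it with the amended sentence so that both documents give one sidedness rule for the exploratory and subset analyses, reported with the 95% confidence intervals already planned. Which sidedness is chosen there matters less than having a single rule.

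The cost is a few sentences, made through the written amendment that protocol 11.3 requires, with no new data and no change to sample size. Exploratory or subset p-values change only if the agreed rule differs from SAP 8.1. The change should be made before the interim unblinding, so that it cannot appear to be driven by results.

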10.4 STUDY ENDPOINTS

10.4.1 Co-Primary Endpoints

- 1) Change in the WOMAC Osteoarthritis Index 3.1 pain sub score as measured by the 5-point Likert scale between Baseline and Week 12.

The primary variable is the average score of the five WOMAC A (pain) subscale questions:

In the last 12 hours, how much pain have you had in the study knee:

1. When walking on a flat surface?
2. When going up or down stairs?
3. At night while in bed? (that is - pain that disturbs your sleep)
4. While sitting or lying down?
5. While standing?

The primary analysis will include the repeated measures of WOMAC A pain sub score from Baseline to Weeks 2, 4, 6, 8, 10, and 12 and will use a mixed-effects model with repeated measures MMRM model, with Treatment assignment, Week, and Baseline WOMAC A pain sub score as fixed effects, and including patient ID as a repeated measure with a compound symmetric covariance matrix for residuals.

- 2) Change in the WOMAC Osteoarthritis Index 3.1 function sub score as measured by the 5-point Likert scale between Baseline and Week 12.

The primary variable is the average score of the seventeen WOMAC C (function) subscale questions.

The primary analysis will include the repeated measures of WOMAC C function sub score from Baseline to Weeks 2, 4, 6, 8, 10, and 12 and will use a mixed-effects model with repeated measures, with Week as a fixed effect, and including patient ID as a repeated measure with a compound symmetric covariance matrix for residuals.

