10.3.4 Statistical Analysis of Co-Primary Effectiveness Endpoints

A mixed-effects model with repeated measures (MMRM) will be used to test the main effect of change in WOMAC A weekly pain score (determined as the average of Daily Pain measurements taken at Baseline and Week 12) from Baseline of Ampion vs. saline at 12 weeks. The model will include change from Baseline measures at 2, 4, 6, 8, 10, and 12 weeks. Treatment assignment, week, and Baseline WOMAC A measure will be included as fixed effects. Patient ID will be included to capture repeated measures using a compound symmetric covariance matrix for residuals. The primary hypothesis test for pain is the change in pain at 12-weeks at the one-sided $\alpha = 0.025$ level.

The same model will be used to test the effect of WOMAC C function change from Baseline of Ampion vs. saline at 12 weeks. WOMAC C will be tested at one sided $\alpha = 0.025$. Because both endpoints have to achieve statistical significance, this pairing ensures the one-sided Type I error control at the 0.025 level.

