10.3.9 Interim analysis

There will be one interim analysis once 724 subjects have reached the primary endpoint assessment at Week 12.

At the interim analysis, the conditional probability based upon the observed treatment WOMAC C function score will be calculated. The minimal conditional probability that allows a sample size increase without inflating Type I error under the promising zone for a sample size increase up to 150% is 0.391. Any conditional power < 0.391 results in going to 1,034 patients, randomized 1:1 for Ampion and saline IA injection. Sample size re-estimation according to the promising zone is done for conditional powers between 0.391 and 0.90 with a sample size increase capped to a maximum of 1,552 total patients, randomized 1:1 for Ampion and saline IA injection. A conditional power $> 90\%$ results in enrolling to 1,034 patients.

The final analysis, defined by a sample size established using the promising zone, will use the critical value with one-sided $\alpha = 0.025$ for WOMAC A (Ampion vs. saline control) and WOMAC C (Ampion vs. saline control).

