### 8.6.1 Primary Effectiveness Endpoints

Change in WOMAC A pain score as measured by a 5-point Likert scale, from Baseline to Week 12, will be analyzed by including change from Baseline at 2, 4, 6, 8, 10, and 12 weeks in a mixed-effects model with repeated measures (MMRM). Treatment assignment Week, the treatment\*week interaction and Baseline WOMAC pain score will be included as fixed effects. Patient ID will be included to denote repeated measures and a compound symmetric covariance matrix will be used for residuals. Least squares means and treatment difference with 95% confidence intervals will be presented.

SAS code used will follow the following format:

```
Proc mixed;
  Class PtID treatment week;
  Model delta_pain = treatment baseline_pain week treatment*week;
  Repeated week / subject=newID type = CS;
  Lsmeans active*week / SLICE=week diff;
run;
```

The primary analysis will include the repeated measures of WOMAC C function sub score from Baseline to Weeks 2, 4, 6, 8, 10, and 12 and will use a mixed-effects model with repeated measures MMRM model, with Week as a fixed effect, and including patient ID as a repeated measure with a compound symmetric covariance matrix for residuals.

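### Compound symmetry makes the Week 12 WOMAC C test depend on an unchecked equal-variance assumption; stating the full model with an unstructured covariance is a cheap improvement

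*Protocol*

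**What the plan says.** - **Function, covariance.** Protocol 10.4.1 fits WOMAC C "with Week as a fixed effect, and including patient ID as a repeated measure with a compound symmetric covariance matrix for residuals". SAP 8.6.1 repeats this, "including patient ID as a repeated measure with a compound symmetric covariance matrix for residuals". The only fixed effect named in these two sentences is Week.
- **Function, by reference to pain.** Protocol 10.3.4 says "The same model will be used to test the effect of WOMAC C function change from Baseline of Ampion vs. saline at 12 weeks". The pain model there has treatment, week and baseline as fixed effects, with no interaction. SAP 3.4 lists the same three terms.
- **Visits.** "The model will include change from Baseline measures at 2, 4, 6, 8, 10, and 12 weeks".
- **Interaction.** It appears only for pain, in the SAP 8.6.1 text and code: "Model delta_pain = treatment baseline_pain week treatment*week". That code also sets type = CS.
- **PGA.** Protocol 10.4.2 uses a similar model, "including patient as a repeated measure with a compound symmetric covariance matrix for residuals". SAP 8.6.2 fits it over seven visits including Week 24. Neither names a treatment-by-week term.
- **Error control.** Protocol 10.3.4 states: "Because both endpoints have to achieve statistical significance, this pairing ensures the one-sided Type I error control at the 0.025 level".

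Neither document gives a sandwich standard error, an alternative structure, a check of the covariance, or an SD by visit for any endpoint. The only SD stated is 0.85, for pain.

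**The concern.** The function hypothesis concerns the change at Week 12, so the natural test is the Week 12 contrast from a model with treatment-by-week. Under compound symmetry that contrast is judged against a variance pooled over Weeks 2 to 12. If the Week 12 residual variance is above the pooled value, the standard error is too small and the test is too liberal. If it is below, the test is conservative.

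WOMAC C is a single reading at each visit. A reading two weeks after Baseline may well track Baseline more closely than one at twelve weeks, and the residual variance of change would then rise over time. That is plausible, but the documents do not show it.

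Function is the endpoint to get right: it sets the sample size (984 against 690 for pain, Protocol 4.1) and is the endpoint used for the interim decision (Protocol 3.3 and 10.3.9).

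**Working it through.** **1. The plan's own figures.** For pain, with difference 0.83 − 0.62 = 0.21, SD 0.85, one-sided 0.025 and 90% power:

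n per arm = 2 × (1.960 + 1.282)² × (0.85/0.21)² = 344.3, so 345, or 690 in total. This matches Protocol 4.1.

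For function, 984 can only be inverted, because no effect or SD is given. The implied standardized effect is √(2/492) × 3.2415 = 0.207. The pain figure comes from a plain two-sample comparison at Week 12, with no borrowing across visits.

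**2. What compound symmetry does to the Week 12 variance.** Missing co-primary scores are imputed (Protocol 10.5), so each analysed dataset is complete. Let S be the pooled residual covariance over k visits. The compound-symmetry total variance is [MSB + (k − 1)MSW]/k, where MSB = 1′S1/k and MSW = (tr S − 1′S1/k)/(k − 1). This reduces to tr S/k, the mean of the visit variances. With r = Week 12 variance / mean visit variance:

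one-sided error = 1 − Φ(1.96/√r)

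At r = 1 this returns 0.025, the stated level. The formula ignores between-imputation variance, which should be small at the planned 5% dropout.

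| r | 1.96/√r | One-sided error |
|---|---|---|
| 0.90 | 2.066 | 0.019 |
| 1.00 | 1.960 | 0.025 |
| 1.03 | 1.931 | 0.027 |
| 1.08 | 1.886 | 0.030 |
| 1.10 | 1.869 | 0.031 |
| 1.18 | 1.804 | 0.036 |

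Simulation check (517 per arm, six visits, 20,000 replicates, SD rising linearly from Week 2 to Week 12 by a factor of 1.0, 1.2, 1.3 or 1.5): 0.025, 0.038, 0.040 and 0.049, against 0.025, 0.036, 0.041 and 0.050 from the formula.

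**3. A plausible range for r (assumption).** Split a reading's variance into a stable trait T, a slowly varying state S and day noise. Then ρ(t) = T + S·exp(−t/τ) is the correlation with Baseline. With one common baseline slope b = mean ρ, the residual variance is v(t) = 1 − 2bρ(t) + b².

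Example: T = 0.4, S = 0.4, noise 0.2, τ = 12 weeks. From Week 2 to Week 12, ρ is 0.739, 0.687, 0.643, 0.605, 0.574, 0.547 and b = 0.632. Then v is 0.466, 0.532, 0.587, 0.634, 0.674, 0.708, with mean 0.600. So r = 0.708/0.600 = 1.18 and the error is 0.036.

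For τ from 4 to 12 weeks:
- 20% noise (T 0.4–0.6, S 0.2–0.4): r = 1.09 to 1.18, error 0.030 to 0.036.
- 40% noise (T 0.3–0.5, S 0.1–0.3): r = 1.03 to 1.08, error 0.027 to 0.030.

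With no decay r = 1 and there is no error. The schedule tables mark no WOMAC C at Week 10, although Protocol 5.1.9 and the model include it. On five visits the upper end rises to r = 1.21 and 0.038.

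**4. Without the interaction.** A treatment main effect tests the average over visits. Compound symmetry judges that average against MSB, its own between-patient variance. Simulated error is 0.024 to 0.026 whatever the spread. The test keeps its size but no longer addresses Week 12.

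**5. PGA.** As written there is no interaction, so step 4 applies. If treatment-by-week is added and Week 24 stays in the model, the step 3 assumptions give 0.026 to 0.032, because Week 24 raises the pooled variance.

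**The case against.** The strongest reply is that no inflation has been shown. Four stronger readings are tempting, and the documents support none of them.

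- **That change from Baseline is known to spread out over time.** No section gives an SD by visit, and none gives any SD for WOMAC C or PGA. The direction is an assumption, and the error reverses if the Week 12 variance is the smaller one.
- **That the function test, as specified, exceeds 0.025.** The WOMAC C sentences name only Week, so read literally they yield no treatment test. The model that Protocol 10.3.4 carries over from pain has no treatment-by-week term, and a main-effect test keeps its size. The concern applies once the Week 12 contrast required by the hypothesis is put into the model.
- **That PGA has the same problem.** No interaction is named for it, and Week 24 would dilute the effect.
- **That the interim decision is distorted.** Protocol 10.3.9 says only that "the conditional probability based upon the observed treatment WOMAC C function score will be calculated". It does not say that the compound-symmetry fit supplies the interim z-value. If it did, at variance ratios of 1.10 to 1.175 a true conditional power of 0.30 would be reported as 0.35 to 0.39. The error under the promising-zone rule would be 0.029 to 0.033, against 0.023 with equal variances.

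These replies limit the claim. What stands is that the plan fixes a covariance under which a Week 12 test is calibrated only by an equality nobody has checked, and it provides no safeguard.

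**Conclusion.** This is a cheap improvement, not a demonstrated loss of error control. With treatment-by-week in the WOMAC C model, the one-sided error at a fixed sample size is about 0.027 to 0.036 if correlation with Baseline decays as assumed, 0.025 if the Week 12 variance equals the visit average, and 0.019 if it is 10% below. The size depends on the split between trait, state and day noise, which the documents do not give.

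A reader might infer that the whole trial runs at these rates. It does not. Both co-primaries must succeed, so function's error rate becomes the trial's only when pain truly works.

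The recommendation does not depend on the direction of the variance trend: an unstructured covariance tests Week 12 on its own variance either way.

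**What to change.** - In Protocol 10.4.1 and SAP 8.6.1, state the WOMAC C model in full: treatment, week, treatment-by-week and baseline WOMAC C, with the Week 12 contrast as the test. Changing the covariance alone would leave no Week 12 treatment contrast in the written model.
- Use an unstructured covariance (type=UN) with Kenward-Roger degrees of freedom. Prespecify the fallback if it does not converge: heterogeneous Toeplitz, then heterogeneous compound symmetry, with a sandwich standard error.
- Use the same form for the Week 12 PGA contrast in Protocol 10.4.2 and SAP 8.6.2.
- State in Protocol 10.3.9 and SAP 7 that the interim conditional power uses this same WOMAC C fit.

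Cost: a few sentences and a small code change before unblinding. Six visits need 6 × 7/2 = 21 covariance parameters instead of 2, which is trivial with about 1,000 patients. The reported standard error may be slightly larger. The planned sample size does not change.
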